The high-risk non-cardiac surgical population represents a major global healthcare challenge. Recent estimates suggest that 234 million major surgical procedures are performed worldwide each year [1]. Complications following major surgery are a leading cause of morbidity and mortality [2-7]. Sickness absence to undergo surgery is second only to cardiovascular disease in terms of associated long-term mortality [2]. In the overall population, the incidence of post-operative complications and death is low. However, studies from the UK suggest a readily identified high-risk sub-group accounts for over 80% of post-operative deaths but less than 15% of in-patient procedures [5, 6]. In the UK, 170,000 patients undergo high-risk non-cardiac surgery each year [5, 6]. Of these patients, 100,000 will develop significant complications resulting in over 25,000 deaths [5-7]. Advanced age, co-morbid disease, major and urgent surgery are the key factors associated with increased risk [5-7]. This pattern of poor outcomes following major surgery can be readily identified worldwide [2-10]. Patients who develop complications but survive will still suffer reductions in functional independence and a substantial decrease in medium and long-term survival [2-4]. A prospective 13 year observational study of the Whitehall II cohort of 6478 British civil servants aged 35-55 examined the link between diagnoses associated with medical absence from work and long term all-cause mortality [2]. Physician-certified sickness absence attributable to undergoing a surgical operation was associated with a two-fold increased risk of mortality. Apart from circulatory disease, surgery was associated with the highest risk of later death compared to psychiatric, infectious, and respiratory disease. Despite strong evidence of the impact of poor surgical outcomes, our understanding of standards of care for patients undergoing major surgery is limited. In particular, little is known about the availability of critical care resources for non-cardiac surgical patients and the impact of critical care admission on clinical outcomes. Importantly, survival amongst patients who develop postoperative complications varies widely between hospitals, confirming both the potential and the need to improve clinical outcomes in this population [11].

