Patients undergoing planned day-case surgery, cardio-thoracic surgery, neurosurgery, radiological or obstetric procedures.

Centres

We aim to recruit as many European centres as possible. We anticipate that a minimum of 150 hundred centres in ten or more nations will be required. We are hopeful that we can meet or exceed this target through the activities of national lead investigators and the support of key organisations such as the European Society of Intensive Care Medicine and the European Society of Anaesthesiology. Centres will receive an individual report allowing comparison of their dataset to that of their national cohort and of the overall dataset. We hope this will act as an incentive to participate.

Ethics approval

Ethics approval may not be required in all participating nations. National lead investigators will be responsible for clarifying the need for ethics approval and applying for this where appropriate. Centres will not be permitted to record data unless ethics approval or an equivalent waiver is in place. This study is in effect a large scale clinical audit. We expect that in most, if not every participating country, there will be no requirement for individual patient consent as all data will be anonymised and is already recorded as part of routine clinical care.

Data collection and collation

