A realistic data set will be fundamental to the success of the investigation. We have identified the key data points whilst not discouraging centres from participating through an excessive burden of data collection. The reliability of data collection will be analysed formally using K-statistics or intra-class correlation coefficients as appropriate. National co-ordinators may request the addition of a limited number of data points to support the international EuSOS data collection and for subsequent national analyses. All additional data points must be discussed with the chief investigator and if necessary, the steering committee.

Form A: Centre specific data (collect once for each centre)

- Secondary/tertiary centre
- Number of operating rooms
- Number and level of critical care beds.
- Details about the reimbursement status of the hospital
- Public holidays or other local factors affecting patient throughput during study period

Form B: Individual patient data on all patients

Patient factors:

- Age
- Gender
- American Society of Anesthesiologists (ASA) grade
- Date of hospital admission
- Major co-morbid disease including:
 - Heart failure
 - Active cancer
 - Diabetes
 - Asthma / COPD
 - Renal failure

Surgical factors:

- Surgical procedure category
- Grade of surgery (minor, intermediate, major)
- Urgency of surgery (elective or non-elective)
- Duration of surgery (mins)
- Grade of surgeon
- Surgical checklist (Y/N)

Anaesthetic factors:

- Anaesthetic technique (general, regional, sedation)
- Haemodynamic (cardiac output) monitoring
- Airway (endotracheal, laryngeal mask, tracheostomy, etc)
- Grade of anaesthetist

Post-operative care:

- Duration of extended recovery stay (hours)
- Post-operative invasive ventilation within first 24 hours (planned / unplanned)
- Post-operative non-invasive ventilation within first 24 hours (planned / unplanned)
- Post-operative inotrope / vasopressor use within first 24 hours

Follow-up data:

- Date of Hospital discharge
- In-hospital mortality

Form C: Individual patient data for those admitted to critical care**Critical Care admission:**

- Body height and mass
- Critical care admission: Date and time
- Critical care admission: planned/unplanned
- Critical care admission: time since surgery
- Detailed co-morbidities
- Airway at ICU admission (endotracheal, laryngeal mask, tracheostomy, etc)
- Ventilatory support at ICU admission (invasive / non-invasive / none)

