- Respiratory arrest prior to critical care admission
- Cardiac arrest prior to critical care admission
- Component data for SAPS III score
- SOFA score (one of four scores in each of six domains)

Physiological data following 24 hours in critical care:

- SOFA score (one of four scores in each of six domains)
- Respiratory support (invasive or non-invasive)
- Renal replacement therapy (planned or unplanned)

Physiological data following 48 and 72 hours in critical care:

- SOFA score (one of four scores in each of six domains)
- Respiratory support (invasive or non-invasive)
- Renal replacement therapy (planned or unplanned)

Follow-up data for patients admitted to critical care:

- Critical care discharge: Date and time
- SOFA score in last 24 hours of ICU stay (for patients staying ≥ 96 hours)
- Major therapeutic limitation during ICU stay (Y / N, date)
- Critical care discharge: planned or unplanned
- Critical care mortality

Sample size calculation

We anticipate that approximately 20,000 patients will be required to provide a sample of up to 2,000 admissions to critical care after surgery. Assuming an overall mortality rate following surgery of 1%, a sample size of 20,000 patients will yield 200 deaths. This will allow the inclusion of at least fifteen variables in a logistic regression model for mortality. The rate of admission to critical care is likely to vary between nations but an overall rate of 10% (either planned or unplanned) will yield data on 2000 admissions to critical care, whilst an overall rate of 5% will yield 1000 admissions. We expect this to allow a robust logistic regression model for this outcome. 20,000 patients will also provide >99% confidence for the overall mortality rate with 0.37% confidence width. This dataset would also have sufficient generalisability to inform the practice of peri-operative care on an international basis. If 200 deaths are observed in an overall sample of 20,000 patients, the 99% confidence interval for the proportion would be (0.0083 - 0.0120) with a confidence width of 0.37%. This dataset would also have sufficient generalisability to inform the practice of peri-operative care on an international basis.

Statistical analysis

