The data to be collected are all collected as part of routine clinical care. Categorical variables will be described as proportions and will be compared using chi-square or Fisher's exact test. Continuous variable will be described as mean and standard deviation if normally distributed or median and inter-quartile range if not normally distributed. Comparisons of continuous variables will be performed using one-way ANOVA or Mann-Whitney test as appropriate. Uni-variate analysis will be performed to test factors associated with planned and unplanned admission to critical care and / or in-hospital death. A multiple logistic regression model will be used to identify independent risk factors. A stepwise approach will be used to enter new terms into the logistic regression model where $p < 0.05$ was set as the

limit for inclusion of new terms. A logistic regression model will be performed to assess independent association between prognostic factors and outcomes. Results of logistic regression will be reported as adjusted odds ratios (OR) with 95% confidence intervals. A single final analysis is planned at the end of the study.

Primary outcome measure

- In-hospital mortality

Secondary outcome measures

- Duration of hospital stay
- Planned admission to critical care
- Unplanned admission to critical care
- Duration of critical care stay

Organisation

Subject to funding approval, it is proposed that the EuSOS study will be conducted by the EuSOS study group on behalf of the European Society of Intensive Care Medicine and the European Society of Anaesthesiology. The steering committee will be chaired by RP. The study management team will be appointed by the steering committee and led by RP. The duties of this team will include administration of all project tasks, communication between project partners (including funders, steering committee members, national and local co-ordinators, etc), data collation and management and preparation of reports for individual study sites. The Steering committee is responsible for the scientific conduct and consistency of the project. The Steering committee will ensure communication between the funder(s), study management team and co-ordinators as necessary.

National co-ordinators

National co-ordinators will be appointed by the steering committee to lead the project within individual nations and:

- Identify local co-ordinators in participating hospitals
- Assist with translation of study paperwork as required

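### The planned tests and logistic regression make no allowance for clustering in hospitals and nations, so intervals for hospital- and system-level effects will be too narrow, by an amount the Protocol gives no means to judge

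*Protocol*

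**What the plan says.** All the methods are named in the Statistical analysis section of the Protocol. For group comparisons: "Categorical variables will be described as proportions and will be compared using chi-square" or Fisher's exact test, with one-way ANOVA or Mann-Whitney for continuous variables. For risk factors: "A multiple logistic regression model will be used to identify independent risk factors", with stepwise entry at p < 0.05 and odds ratios with 95% intervals. No random effect, GEE, robust variance, stratification or design effect is mentioned anywhere. The one reference to intra-class correlation, under Dataset, concerns the reliability of data collection.

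The sampling is by hospital: consecutive patients within participating centres, and under Centres, "We anticipate that a minimum of 150 hundred centres in ten or more nations will be required" (read here as 150). One form is filled in per hospital: "Form A: Centre specific data (collect once for each centre"; it covers secondary or tertiary status, operating rooms, critical care beds and reimbursement. Research questions 5 and 6 compare health-care systems, and question 7 asks what determines admission to critical care.

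The Protocol itself expects variation at both levels. The background says that "survival amongst patients who develop postoperative complications varies widely between hospitals", and the sample size section says: "The rate of admission to critical care is likely to vary between nations".

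**The concern.** Patients in one hospital share case mix, staffing, bed supply and admission policy, so their outcomes are correlated. For a factor with one value per hospital, the information comes from about 150 hospitals rather than 20,000 patients. For a factor with one value per nation, it comes from about ten nations. A test that counts patients as independent then understates the standard error.

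At stake are the comparative aims. Differences between health-care systems, and hospital characteristics offered as determinants of admission or death, would be declared significant more often than the nominal 5%. The p < 0.05 entry rule would also admit such factors to the model too readily. The stated precision of overall mortality rests on the same assumption, although the sample size section claims that the data will generalise internationally.

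**Working it through.** **1. The plan's own figure.** Input: "Assuming an overall mortality rate following surgery of 1%, a sample size of 20,000 patients will yield 200 deaths". The plan states that "the 99% confidence interval for the proportion would be (0.0083 - 0.0120) with a confidence width of 0.37" per cent. The exact (Clopper-Pearson) 99% interval for 200/20,000 independent patients is 0.00828 to 0.01196, width 0.368%. The figure reproduces and leaves no room for a design effect. The Wald width is 2 × 2.576 × √(0.01 × 0.99 / 20,000) = 0.362%.

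**2. Design effect.** With equal hospital sizes, m = 20,000/150 = 133.3 patients per hospital and DE = 1 + (m − 1) × ICC. The true standard error of a hospital-level effect is √DE times the naive one. The Protocol gives no ICC, so a range is shown.

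| Hospital ICC (assumed) | DE | √DE | True coverage of a 95% interval | 99% Wald width, mortality |
|---|---|---|---|---|
| 0.001 | 1.13 | 1.06 | 93.5% | 0.39% |
| 0.005 | 1.66 | 1.29 | 87% | 0.47% |
| 0.01 | 2.32 | 1.52 | 80% | 0.55% |
| 0.05 | 7.62 | 2.76 | 52% | – |
| 0.10 | 14.23 | 3.77 | 40% | – |

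For ten nations, m = 2,000. A nation ICC of 0.001 gives DE = 1 + 1,999 × 0.001 = 3.0, √DE = 1.73 and a type I error of 26%. An ICC of 0.005 gives 11.0, 3.32 and 55%.

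**3. Simulation at the Protocol's overall rates.** Design: 150 hospitals × 133 patients, random hospital intercept on the logit scale, no true effect, naive Wald test at 5%. The overall rate is held at 1% for death and at 5% and 10% for admission, the figures in the sample size section. The SDs are assumptions. SD 0.5 means a 3.6-fold odds difference between hospitals at the 10th and 90th percentiles (exp(2 × 1.2816 × 0.5)).

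| Null hospital-level factor (75 v 75) | SD 0.3 | SD 0.5 | SD 0.8 |
|---|---|---|---|
| Death, 1%: rejections | about 7% | about 9% | about 19% |
| Death, 1%: SE too small by | 1.07 | 1.16 | 1.49 |
| Admission, 5–10%: rejections | 12–17% | 22–33% | 39–51% |

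| Null nation-level factor (5 v 5 nations), hospital/nation SD 0.3/0.2 to 0.5/0.3 | Rejections |
|---|---|
| Death, 1% | about 16–26% |
| Admission, 5–10% | about 40–67% |

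A repeat with 20,000 runs per setting agreed within about two percentage points: hospital-level death 6.2, 9.5 and 17.6%; nation-level death 15 and 28%; nation-level admission 39 to 66%. The formula agrees too. At 1% mortality these three SDs correspond to ICCs of about 0.0009, 0.0028 and 0.0085, so DE = 1.12, 1.37 and 2.12 and √DE = 1.06, 1.17 and 1.46.

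**4. A named test directly.** A plain chi-square across ten nations was run with hospital variation only and no nation effect, with the median hospital at 8% admission or 1% mortality. It rejected in 43% (SD 0.3) and 86% (SD 0.5) of runs for admission, and in 9% and 20% for death.

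**5. Patient-level factors.** For a patient-level factor balanced over hospitals, ordinary logistic regression gave a type I error of 4 to 6.5% and a ratio of true to naive SE of 0.97 to 1.06 (hospital SDs 0.3 to 1.0, 400 runs per setting).

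**The case against.** The strongest reply is that a statistical analysis plan may exist, that logistic regression does not exclude a multilevel version, and that the variance estimator is often left to that document. This stands for the regression: it is silent on clustering rather than fixed as single-level. It does not cover the chi-square, Fisher, ANOVA and Mann-Whitney tests or the binomial interval, which are fixed here in a form that assumes independence.

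Second, the main use of the model is to find patient risk factors such as age, ASA grade, co-morbidity and urgency. These vary within hospitals, and step 5 shows that their standard errors hold when they are balanced across hospitals. This stands, although unmodelled hospital differences could still confound a factor that is unevenly spread.

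Third, the Protocol does not say that Form A items enter the model, and it never defines a health-care system. Treating it as one value per nation is an inference, since reimbursement is recorded per hospital. The 5 v 5 split of nations is illustrative. This also stands. Any definition tied to hospitals or nations meets the problem, but its size would differ.

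A reader might infer that all the intervals are grossly too narrow, or that null hospital factors are bound to be reported as independent determinants of death. The documents do not support that. They give no ICC, and for hospital-level effects on the primary outcome the standard error is too small by only about 1.07 to 1.49 times under the assumed SDs.

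**Conclusion.** The point holds for effects that vary between hospitals or nations. As described, the analysis ignores clustering that the Protocol itself expects, and error rates for questions 5 and 6 and part of 7 will exceed 5%. The excess is modest for hospital-level effects on death, and large for critical care admission and for most nation-level comparisons. Every size rests on assumed hospital and nation variances, equal hospital sizes and the reading of 150 centres. Variable hospital sizes would raise the inflation: at ICC 0.01, a coefficient of variation of 0.8 in hospital size takes √DE from 1.52 to 1.78.

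Point estimates of the descriptive results are not in question. Nor is the arithmetic of the mortality interval, which is correct for independent patients. The interval is too narrow only as a statement about hospitals beyond those taking part.

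**What to change.** In Statistical analysis, state that the logistic models for death and for critical care admission account for clustering by hospital and nation. Random intercepts for hospital within nation are one way; GEE or cluster-robust variance by hospital are others, and the choice is the sponsor's. For comparisons between nations, systems or hospital types, replace the plain chi-square, ANOVA and Mann-Whitney tests with model-based or cluster-adjusted tests. Use small-sample degrees of freedom where a factor varies only between nations.

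In Sample size calculation, say that the 0.37% width assumes no clustering, or give it over a range of ICCs (about 0.39 to 0.55% at hospital ICC 0.001 to 0.01).

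No new data are needed, because each centre already has a numeric code under Data collection and collation. The cost is a change of wording, slightly more analysis work, and wider intervals for hospital and system effects.

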Appendix: Definitions

Anaesthetic technique

General anaesthesia: Pharmacologically induced state of unconsciousness in order to facilitate surgical procedure

Sedation: Pharmacologically induced reduced level of consciousness during which verbal contact is maintained

Regional anaesthesia: injection or infusion of a clinically effective dose of local anaesthetic and / or opioid drugs in order to provide clinically effective anaesthesia

Severity of surgery

Minor: Procedure of less than 30 minutes duration performed in a dedicated operating room which would often involve extremities or body surface or brief diagnostic and therapeutic procedures.

Examples include: *arthroscopy without intervention, removal of small cutaneous tumour, diagnostic proctology procedures, biopsy or excision biopsy of small lesions, etc*

Intermediate: More prolonged or complex procedure performed in a dedicated operating room that may pose the risk of significant complications or tissue injury.

Examples include: *laparoscopic cholecystectomy, arthroscopy with intervention, bilateral varicose vein removal, tonsillectomy, inguinal hernia repair, breast lump resection, haemorrhoidectomy, appendicectomy, partial thyroidectomy, cataract surgery, uvuloplasty, minimally invasive repair of vaginal prolapse, vaginal hysterectomy, tendon repair of hand, fixation of mandibular fracture, etc*

Major: Any surgical procedure that requires anaesthesia, performed in a dedicated operating room and is expected to last more than 90 minutes.

Examples include: *major gut resection, major joint replacement, mastectomy, extensive head and neck tumour resection, abdominal aortic aneurysm repair, major vascular bypass procedure, procedures involving free flap to repair tissue defect, amputation, total thyroidectomy, cystectomy, trans-urethral resection of prostate, resection of liver tumour, carotid endarterectomy, nephrectomy, total abdominal hysterectomy, spinal discectomy, etc*

Urgency of surgery

Elective: Not immediately life saving; planned within months or weeks
Non-elective: As soon as possible after resuscitation and ideally within 24 hours

American Society of Anesthesiologists (ASA) score:

- I A normal healthy patient
- II A patient with mild systemic disease which does not limit physical activity
- III A patient with severe systemic disease which limits physical activity
- IV A patient with severe systemic disease that is a constant threat to life
- V A patient who is not expected to survive for 24 hours without the operation

Duration of surgery

Time in minutes from induction of anaesthesia to patient leaving the operating room

Post-anaesthetic recovery unit

A post-anaesthetic recovery unit is dedicated facility for the care of all patients following surgery under anaesthesia. This does not include units which routinely care for invasively ventilated patients overnight. Duration of stay is the time from arrival to departure measured in minutes.

Post-operative Critical Care

For this study, a critical care unit is defined as a facility routinely capable of admitting patients who require invasive ventilation overnight. This differs from a post-anaesthetic recovery unit which has a primary purpose to provide care for all patients after anaesthesia regardless of dependency. Duration of stay is the time from arrival to departure measured in hours (part hours to count as one whole hour).

Duration of hospital stay

Time in days from the day of surgery to the day the patient leaves hospital. This will not be adjusted for delays relating to provision of social care in the community.

Haemodynamic (cardiac output) monitor

Any technology which provides a measurement of cardiac output. This would include oesophageal Doppler, pulmonary artery catheter and arterial waveform analysis but not devices which solely estimate arterial pressure variability.

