Little is known about standards of care for patients undergoing major non-cardiac surgery across Europe or clinical outcomes following such procedures. It has been suggested by some that poor surgical outcomes may vary between nations but this belief may simply reflect better recognition of the issue. Evidence from sources across the developed world suggests the existence of a large population of patients who can be readily identified as being at high risk of post-operative complications and death [2-10]. There is increasing recognition of the massive potential impact of even small improvements in peri-operative care [17, 18]. However, significant policy change can only be driven by robust and powerful data. Mismatch between critical care resource provision and peri-operative risk may be widespread or confined to a small number of nations. Either way, a rigorous evaluation of standards of peri-operative critical care across Europe would provide important data which could trigger a step-change in the current approach to care of the patient undergoing major non-cardiac surgery.

Research questions

1. What is the in-hospital mortality rate for patients undergoing non-cardiac surgery in Europe?
2. What is the duration of hospital stay for patients undergoing non-cardiac surgery in Europe?
3. What is the current standard of peri-operative critical care provision for patients undergoing non-cardiac surgery in Europe?
4. What is the current standard of haemodynamic (cardiac output) monitoring for patients undergoing non-cardiac surgery in Europe?
5. Is there any evidence of differences in the standard of peri-operative care provision for patients undergoing non-cardiac surgery in different health-care systems within Europe?
6. Is there any evidence of differences in hospital stay and mortality for patients undergoing major non-cardiac surgery in different health-care systems within Europe?
7. What factors determine planned and unplanned admission to critical care after surgery?
8. Are the factors associated with critical care admission similar to those associated with post-operative death?

Methods

Seven day, international cohort study of adult (≥ 16 years) patients undergoing in-patient non-cardiac surgery.

Inclusion criteria

Consecutive patients admitted to participating centres undergoing elective and non-elective non-cardiac surgery commencing during the seven day study period (00⁰⁰ day 1 to 24⁰⁰ day 7) with a planned overnight stay.

Exclusion criteria

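### Duration of hospital stay is counted from the day of surgery, but the Form B items listed for all patients include no date of surgery

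*Protocol*

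**What the plan says.** The Appendix to the Protocol defines duration of hospital stay as "Time in days from the day of surgery to the day the patient leaves hospital". The Protocol lists "Duration of hospital stay" among its secondary outcome measures. Research question 2 asks "What is the duration of hospital stay for patients undergoing non-cardiac surgery in Europe", and research question 6 asks whether stay and mortality differ between European health-care systems.

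The Dataset section sets out three forms:

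- **Form A** is completed once per centre and holds no patient dates.
- **Form B** covers all patients. Its calendar items are "Date of hospital admission" and "Date of Hospital discharge". Its only timing item for the operation is duration in minutes.
- **Form C** covers critical care patients only. It lists the date and time of critical care admission and the time elapsed since surgery.

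On a smaller matter, Form B asks for extended recovery stay in hours. The Appendix entry for the post-anaesthetic recovery unit says "Duration of stay is the time from arrival to departure measured in minutes".

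**The concern.** The defined outcome needs two dates, and the list for all patients supplies only the second. If data were collected exactly as listed, the analyst would have admission-to-discharge stay for most of the cohort. That measure includes any days in hospital before the operation, which the protocol's definition leaves out.

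This matters most for research question 6. If hospitals or countries differ in how long before surgery they admit patients, that difference would enter the stay comparison and could be read as a difference after surgery. An analysis plan cannot repair this, because it cannot supply a date that was never recorded.

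**Working it through.** The protocol states no figure to reproduce here. The check compares the listed items with the definition.

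**1. What the definition needs.** Let A be the admission date, S the surgery date and D the discharge date. The defined stay is D − S.

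**2. What the forms give.**

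| Item | Form B (all patients) | Form C (critical care only) |
|---|---|---|
| A | listed | – |
| D | listed | – |
| S | not listed | derivable: date and time of critical care admission minus time since surgery |

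**3. How many patients lack S.** The Sample size calculation section plans 20,000 patients and considers critical care admission rates of 10% and 5%.

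- At 10%: 20,000 × 0.10 = 2,000 with Form C, leaving 20,000 − 2,000 = 18,000 (90%) without.
- At 5%: 20,000 × 0.05 = 1,000 with Form C, leaving 20,000 − 1,000 = 19,000 (95%) without.

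**4. What is available for the rest.** The listed dates give D − A, and D − A = (D − S) + (S − A). The excess over the defined outcome is S − A, the pre-operative stay. It is never negative. The inclusion criteria require surgery to start within the study week but do not require admission within it, so S − A has no upper limit in the protocol.

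**5. Whether the study week recovers S.** Number the study days 1 to 7. S must lie between the later of A and day 1, and the earlier of D and day 7. This narrows the range but rarely fixes the date. A patient admitted on day 3 and discharged on day 5 could have been operated on on day 3, 4 or 5, so the defined stay is 2, 1 or 0 days. The date is fixed only where the two limits meet: admission on day 7, discharge on day 1, or admission and discharge on the same day. The protocol does not say how many patients would fall there.

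**6. Recovery stay.** Form B uses hours and the Appendix uses minutes. Form B speaks of extended recovery, which the Appendix does not define separately, so it is unclear whether the two describe the same quantity.

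**The case against.** The best defence is that the Dataset section is an outline and not the case report form. It presents its items as the key ones, and some entries, such as the components of the SAPS III score, stand for several fields. The form itself is not shown and may well include the date. Each centre must also know the operation date in order to decide eligibility. The Data collection section keeps identifiable paper forms and a patient list at each centre, partly so that missing items can be supplied later. All of this stands. It shows that the date exists and could be retrieved. It does not remove the mismatch between the protocol's list and its own definition, and retrieval afterwards would mean returning to some 18,000 to 19,000 records.

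A reader might infer several stronger points that the document does not support:

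- **That the outcome cannot be computed at all.** It can be derived for patients with Form C, and an omission from the protocol's list does not prove that the study fails to collect the date.
- **That one typical error in days can be stated for everyone, with surgery taken as equally likely on each of the seven days.** The protocol gives no such distribution, and the admission and discharge dates narrow the range differently for each patient.
- **That mortality results suffer.** No mortality analysis at a fixed time after surgery is planned, and in-hospital mortality needs no surgery date.
- **That the unit mismatch will corrupt recovery data by the ratio of minutes to hours.** The Form B label itself asks for hours, the two entries may not mean the same thing, and recovery stay is not a listed outcome.

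**Conclusion.** The point holds as a mismatch between a named secondary outcome and the dataset meant to supply it. On the listed items, the outcome as defined is generally derivable only for the 5% to 10% of patients with Form C, apart from the few date patterns that the study week happens to settle. The other 90% to 95% would have a different, longer measure.

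The count assumes the planned 20,000 patients, the protocol's own critical care rates, and that the case report form follows the list as written. The size of any distortion between health-care systems cannot be given, because the protocol reports no pre-operative stay and no variation in it; that it could arise is an inference. Research question 2 is affected directly. Research question 6 is affected only in its stay component. The sample size reasoning and the critical care admission outcomes are untouched. The recovery-stay unit is an editorial matter.

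**What to change.** Add the date of surgery to Form B for every patient and derive duration of hospital stay from it. If the case report form already carries the date, say so and correct the list in the Dataset section. Do this before the forms are translated and validated in each nation. The cost is one date field that every centre already knows.

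Redefining stay from admission would also remove the contradiction, but it would give up the post-operative measure that the protocol chose.

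In the same revision, use one unit for recovery stay on Form B and in the Appendix, or define extended recovery separately with its own unit.
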